8.1.2 Key Secondary Efficacy Definitions

- RECIST responses for patients with measurable disease at baseline (RECIST guidelines v1.1, Eisenhauer et al., 2009)

- Overall Response Rate (ORR) = Proportion of patients with a best overall response (BOR) of Complete Response (CR) or Partial Response (PR). ORR is based on RECIST v1.1 response for patients with measurable disease at baseline.

Patients with no evaluable RECIST evaluations after baseline will be considered non-responders.

Soft tissue CR or PR needs to be confirmed at the next scan that is evaluable at least 4 weeks later. The following rules will be taken into account to define the BOR:

- CR = at least two determinations of CR at least 4 weeks or later
- PR = at least two determinations of PR or better (i.e. CR) at least 4 weeks or later apart (and not qualifying for CR)
- SD = at least one Stable Disease (SD) assessment or better (i.e. CR or PR) > 6 weeks after first dose of randomized treatment (and not qualifying for CR or PR)
- Non-CR/Non-PD = at least one non-CR/non-PD assessment (or better) > 6 weeks after first dose of randomized treatment (and not qualifying for CR or PD).
- PD = Progressive Disease (PD) at first evaluable scan after first dose of randomized treatment (and not qualifying for CR, PR or SD)
- Disease Control Rate (DCR) = Proportion of patients with BOR of CR, PR, SD, or Non-CR/Non-PD according to RECIST v1.1.
 - Same rules for no post baseline evaluations and for confirmation of CR and PR
 - Also, best response of SD or Non-CR/No-PD must be at least 6 weeks after date of first dose.

Duration of response (DOR) (months) (only for patients with a tumor response of CR or PR): (Date of RECIST PD/death/censor – Date of Best Overall Response + 1)/30.4375.) DOR is defined as the duration between the date of first documented best overall response and the date of first documented radiographic progression or death due to any cause. Date of Best Overall Response is the date of the first RECIST response of CR or PR of the confirmed response endpoint Overall Response Rate. Censoring rules are the same as for rPFS, except using only soft tissue scan dates (excluding bone scan dates).

- Time to first symptomatic skeletal event (SSE, months): (Date of SSE/censor – Date of randomization + 1)/30.4375. Time to first SSE is defined as the time (in months) from the date of randomization to the date of the SSE or death from any cause. SSE date is date of first new symptomatic pathological bone fracture, spinal cord compression, tumor-related orthopedic surgical intervention, requirement for radiation therapy to relieve bone pain, or death due to any cause, whichever occurs first. SSE

data for this endpoint is collected up through EOT visit.

Censoring date is date of the last study visit (on or before EOT visit).

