Investigational product:	
Patients randomized to receive the investigational product will receive 7.4 GBq ($\pm 10\%$) ^{177}Lu-PSMA-617 intravenously every 6 weeks (± 1 week) for a maximum of 6 cycles. After 4 cycles, patients will be assessed for (1) evidence of response, (2) residual disease, and (3) tolerance to ^{177}Lu-PSMA-617. If the patient meets the criteria above and agrees to continue with additional treatment of ^{177}Lu-PSMA-617 radioligand therapy, the investigator may administer 2 additional cycles. A maximum of 6 cycles of radioligand therapy is allowed. After the last cycle of ^{177}Lu-PSMA-617, patients can continue best supportive/best standard of care alone. If the patient does not meet all of the criteria or does not agree to additional ^{177}Lu-PSMA-617 treatment, then no additional doses of ^{177}Lu-PSMA-617 will be administered after Cycle 4. These patients can continue on best supportive/best standard of care alone after Cycle 4.

Assessment schedule:	
Radiographic imaging will be done every 8 weeks (± 4 days) during the first 24 weeks of treatment and every 12 weeks (± 4 days) thereafter, regardless of treatment delays, through the End of Treatment visit.
 
The previous 2 PSA values will be noted before randomization. Serum/plasma testosterone and PSA levels will be measured up to 3 days prior to Day 1 of each cycle. Hematology and chemistry will be done weekly during Cycle 1 (up to 3 days prior to each time point) and up to 3 days prior to Days 1, 15, and 29 in Cycles 2 to 6 (i.e. every two weeks). After Cycle 6, hematology and chemistry will be done every 12 weeks (± 4 days) until the patient starts long-term follow-up.
 
Patients will complete the BPI-SF, EQ-5D-5L and FACT-P questionnaires about their pain level and HRQoL during screening and prior to treatment on Day 1 of

	
each cycle and through the End of Treatment visit. Patients will be monitored throughout the study for SSEs.
 
After the final analysis of OS, patients in the active part of the study will have an end of treatment (EOT) visit and move into long-term follow-up. Long-term follow-up will be extended on this study until a long-term safety follow-up study is available in the respective country (estimated in 2nd quarter of 2023).

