2.2.2 Key Secondary endpoints

The key secondary endpoints include the following:

1. RECIST response to include:
 - a. Objective response rate (ORR) (CR + PR) as measured by RECIST v1.1 response in soft tissue, lymph node and visceral lesions. Duration of Response (DOR) will also be measured in patients with a CR or PR from date of first response to the date of RECIST progression or death.
 - b. Disease Control Rate (DCR) (CR + PR + stable disease [SD]) as measured by RECIST v1.1 response in soft tissue, lymph node and visceral lesions.
2. The time to a first SSE defined as date of randomization to the date of first new symptomatic pathological bone fracture, spinal cord compression, tumor-related orthopedic surgical intervention, requirement for radiation therapy to relieve bone pain or death from any cause, whichever occurs first.

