If the patient meets all of the criteria above, and agrees to continue with additional treatment of ¹⁷⁷Lu-PSMA-617, the investigator may administer a further 2 cycles. A maximum of 6 cycles of radioligand therapy is allowed. If the patient does not meet any of the criteria or does not agree to additional ¹⁷⁷Lu-PSMA-617 treatment, then no additional doses of ¹⁷⁷Lu-PSMA-617 will be administered after Cycle 4. After the last cycle of ¹⁷⁷Lu-PSMA-617, patients can continue BSC/BSoC alone.

BSC/BSoC for each patient will be selected at the discretion of the patient's physician, prior to randomization and will be administered per the physician's orders and continued until the patient comes off the treatment part of the study and enters the long-term follow-up stage.

A patient may choose to discontinue the randomized treatment part of the study at any time. If a patient chooses only to discontinue from the randomized treatment in the study for a reason other than radiographic progression, the patient will be asked to confirm if they consent to continue to be followed for long term safety, radiographic Progression-Free Survival (rPFS), and survival follow up. The patient will continue to be followed for long term follow up unless they specifically withdraw consent from long term follow-up of the study. Crossover to ¹⁷⁷Lu-PSMA-617 treatment is not allowed.

An End of Treatment (EOT) visit should occur once a patient discontinues randomized treatment for any reason (patient or investigator decision, going on to long term follow up, etc.). The EOT visit should occur approximately 30 days from the last dose of ¹⁷⁷Lu PSMA-617 or the date of the best supportive/best standard of care end of treatment decision (whichever is later), but before the initiation of subsequent anti-cancer treatment, outside of what is allowed on study.

After the EOT visit, patients will enter the long-term follow-up period. The long-term follow-up period will include the collection of rPFS (if discontinuing for reasons other than radiographic progression), survival and information about new treatments, along with the patient's response to these treatments, adverse events assessment, and results of hematology and chemistry testing. During follow-up, patients will be followed for safety and survival. They will be contacted every 3 months (± 1 month) via phone, email, or letter for up to 24 months or until 508 deaths have occurred, whichever is sooner.

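### Time to first SSE: SAP 8.1.2 gives deaths no stated limit but ends SSE collection and censoring at the EOT visit, so one common horizon has to be stated

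*SAP*

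**What the plan says.** SAP 8.1.2 runs the endpoint from randomization "to the date of the SSE or death from any cause". The sentence defining the SSE date lists four kinds of skeletal event and closes with "or death due to any cause, whichever occurs first". The SAP then states that SSE "data for this endpoint is collected up through EOT visit", and for patients without an event, "Censoring date is date of the last study visit (on or before EOT visit". No limit for deaths is written down.

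SAP 3.1 times the EOT visit at about 30 days from the last Lu-PSMA-617 dose "or the date of the best supportive/best standard of care end of treatment decision (whichever is later". It continues: "After the EOT visit, patients will enter the long-term follow-up period". Survival is collected in that period, so deaths after EOT are in the database.

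Protocol 2.2.2 ends its own definition with "requirement for radiation therapy to relieve bone pain or death from any cause, whichever occurs first". The assessment schedule in the protocol summary says "Patients will be monitored throughout the study for SSEs".

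Under SAP 8.2.2 the endpoint is analyzed in the PFS-FAS with a two-sided stratified log-rank test. The tables there allow key secondary testing only once OS is met.

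**The concern.** Three horizons should match and, as written, do not: deaths have no stated limit, while SSE collection and censoring end at EOT. Take two patients without an SSE at EOT. The one who later dies is an event on his death date and counts as at risk until then. The one who survives is censored back at his last visit on or before EOT. Presence in the risk set after EOT therefore depends on a future death, which a valid censoring rule cannot allow.

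Two forces follow. The arm that reaches EOT sooner has more follow-up in which only future deaths remain at risk, which raises its apparent hazard. It also loses more SSEs that occur after EOT, which lowers it. If time to EOT differs by arm, the two forces need not cancel, and the HR and p-value of a key secondary endpoint are distorted. Separately, two programmers could build different event sets from the same text.

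**Working it through.** **1. Does another section settle it?**
- For rPFS, SAP 8.1.1 says how long death can count (24 weeks past the last scan). DOR and PFS take over the rPFS censoring rules (SAP 8.1.2, 8.1.3).
- SSE has its own censoring sentence and no such window.
- SAP 8.2.2 carries over the rPFS analysis method to SSE, not its censoring rule.

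**2. Check of the design inputs.** The plan gives no event count or power for SSE. The inputs reused below reproduce the stated power with power = Φ(√(d × 2/3 × 1/3) × |ln HR| − z):
- OS: √(508 × 2/9) × 0.3139 − 2.054 = 1.281, power 0.900 (stated: at least 90%).
- rPFS: √(364 × 2/9) × 0.4055 − 2.652 = 0.995, power 0.840 at HR 4/6, or 0.829 at HR 0.67 (stated: 84%).

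**3. Simulation inputs.**
- From SAP 3.4 and 3.2: 557 patients, 2:1, median OS 10 months, median rPFS 4 vs 6 months.
- Assumed: exponential times; EOT one month after progression; SSE median 12, 18 or 30 months; follow-up of 13 to 20 months at the final OS cut-off.
- Progression hazard = ln2/rPFS median − ln2/OS median: control 0.1733 − 0.0693 = 0.1040 per month; active 0.1155 − 0.0693 = 0.0462. The resulting EOT medians are 4.6 vs 6.4 months.
- Protocol 1.1 cites 49% with a serious skeletal event within 2 years. As a constant hazard this is −ln(0.51)/24 = 0.028 per month, a median of 24.7 months, inside the assumed range.

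**4. No true effect on SSE or death, unstratified** (SSE median 12 / 18 / 30 months):

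| Rule | HR |
|---|---|
| Literal, final OS cut-off | 0.948 / 0.922 / 0.896 |
| Literal, rPFS/interim cut-off | 0.939 / 0.923 / 0.900 |
| SSEs, deaths and censoring all end at EOT (final) | 0.998 to 0.999 |
| Only the censoring date moved to last contact (final) | 1.085 / 1.066 / 1.046 |

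Under the literal rule, deaths after EOT make up 17 / 20 / 22% of events at the final cut-off. One stratified run, with 16 strata of assumed prevalence and prognostic effect and SSE median 18, gave a literal HR of 0.949 and 1.007 with the EOT horizon.

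A separate set-up had EOT medians of 4 vs 6 months independent of death and an SSE hazard of 0.028. It gave a literal HR of 0.935, and 1.00 under either single horizon (EOT or data cut-off).

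**5. When the lean disappears or reverses** (literal rule, no true effect):
- Equal rPFS, 6 vs 6: HR 1.00.
- SSE median 6 months: 0.999; 4 months: 1.03.
- Follow-up of 25 to 32 months, SSE medians 8 / 12 / 18: 1.05 / 1.02 / 0.99.
- Active reaching EOT first (medians 6 control vs 4 active reversed from the separate set-up): 1.07.

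**6. Planned OS effect (10 vs 13.7 months), no SSE effect.** The literal HR is 0.83 / 0.79 / 0.75, against 0.85 / 0.83 / 0.80 with one horizon or complete follow-up. The lean is 0.02 / 0.04 / 0.05. With equal rPFS it goes towards control (0.87 / 0.86 / 0.84).

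**7. Effect of the OS gate.** With no true effect and OS required first, SSE is rejected at one-sided 0.024 in 1.0 to 1.8% of trials under the literal rule, against 0.6 to 0.9% with complete follow-up. Both are below 2.4%.

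**The case against.** The strongest reply is that a single horizon is already there. Death sits inside the SAP's definition of the SSE date, so the statement that SSE data stop at EOT may cover deaths too, and censoring stops there as well. On that reading the bias is nil. This stands as a possible reading, but SAP 8.1.2 never says that deaths after EOT are ignored.

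Other replies also carry weight:
- The conflict with the protocol summary's monitoring sentence is weak. The long-term follow-up columns of Protocol Tables 4 and 6 list no SSE item, which fits an EOT horizon.
- SSE is not the only endpoint of this kind. The time-to-worsening endpoints in SAP 8.2.3.3 and time to first opioid use in 8.2.3.4 also count death without a window. Those are not alpha-controlled.
- An EOT horizon has its own bias if EOT is related to outcome: null HR 1.04 to 1.05 at correlation 0.2 and 1.12 to 1.13 at 0.5, where the literal rule gives 0.91 to 0.96 and 0.92 to 0.97.

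A reader might infer that the rule favors the active arm. The documents do not support that as a general statement. They give no EOT times. Earlier EOT in control is inferred from the planned rPFS medians and from treatment ending at progression or at a disallowed regimen (SAP 5). The early control dropout in SAP 3.1 points the same way but prompted measures effective 5 March 2019, when the PFS-FAS begins. Even earlier control EOT is not sufficient, as step 5 shows.

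**Conclusion.** The point holds as a defect in the stated rule. SAP 8.1.2 leaves two readings open. They give different event sets, and the literal one keeps patients at risk after EOT only if they die. This should be fixed.

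The size is conditional. With EOT tied to rPFS medians of 4 vs 6 months and SSE medians of 12 to 30 months, the null HR is about 0.95 to 0.90 unstratified, and about 0.95 in the one stratified run. With the planned OS effect the lean is about 0.02 to 0.05 in HR. These figures rest on exponential times, an assumed EOT lag and assumed SSE rates. Confidence is high on the text and medium on the size.

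A reader might also infer an inflated Type I error for the testing procedure. The OS gate in SAP 8.2.2 does not support that: simulated null rejection stays below nominal. The harm is a distorted SSE estimate and p-value.

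**What to change.** In SAP 8.1.2, apply one horizon alike to SSEs, deaths and censoring, and reconcile it with Protocol 2.2.2 and the protocol summary. The version needing no new data counts SSEs and deaths only through the EOT visit, timed as in SAP 3.1, and censors everyone else at the last visit on or before EOT.

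As sensitivity analyses, run the version that counts deaths after EOT and an informative-censoring analysis, for example with inverse-probability-of-censoring weights. Report by arm the time to EOT and the deaths before and after it.

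Do not only move the censoring date to last contact while SSE collection stops at EOT; step 4 shows that this reverses the bias. A horizon beyond EOT would need dated SSEs after EOT. SSEs come from three CRFs (SAP 8.2.3.4), and after EOT the SAP describes only adverse event term and grade (9.2.6) and post-treatment radiotherapy (9.8).

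The cost is SAP wording and programming. Protocol 8.2 may call for an amendment, because the method for a key secondary hypothesis changes. The EOT horizon has fewer events (295 against 423 with complete follow-up at SSE median 18). Power is lower: 66 to 76% against 86 to 89% if SSE and death both have HR 0.73. It can lean towards control if EOT is related to outcome.

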8.1.3 Additional Secondary Efficacy Definitions

- Progression-free survival (PFS) (months): (Date of first radiographic progression/clinical progression/PSA progression/death/censor – Date of randomization + 1)/30.4375. PFS is defined as the time (in months) from the date of randomization to the date of first evidence of radiographic, clinical or PSA progression or death due to any cause, whichever occurs first. The dates of radiographic, clinical and PSA progression are defined as follows:
 - Date of radiographic progression: defined in Section 8.1.1.
 - Date of clinical progression: earliest date of assessment for when the investigator indicates clinical progression has occurred.
 - Date of PSA progression: Where a decline from baseline is documented, date that a $\geq 25\%$ increase in PSA and an absolute increase of 2 ng/mL or more from the nadir (from all scheduled and unscheduled visits prior to the current visit being evaluated) is documented and confirmed by a second value obtained 3 or more weeks later. Rises in PSA within the first 12 weeks of date of first dose of randomized treatment will be ignored.
Where no decline from baseline is documented, PSA progression is defined as a $\geq 25\%$ increase from the baseline value along with an increase in absolute value of 2 ng/mL or more after 12 weeks from the date of first dose of randomized treatment (with confirmation obtained 3 or more weeks later) as specified in PCWG3 guidelines.
 - Date of censoring for PFS: Censoring date is the same as defined for rPFS.
- PSA doubling time (months): PSA doubling time will be calculated as natural log of 2 (0.693) divided by the sum of the fixed slope (common to all patients) and the random slope (specific for the patient) of the random coefficient linear model between the natural log of PSA and time of PSA measurement (Svatek et al., 2006). If the PSA doubling time is less than zero (i.e. stable, nonincreasing, or decreasing PSA levels as defined by a negative slope from the random coefficient linear model), the PSA doubling time is set to zero. The calculation will be based on (1) latest baseline PSA measurement ≥ 0.2 ng/mL, (2) at least three consecutive (scheduled and unscheduled) post-baseline PSA values with each value ≥ 0.2 ng/mL, and (3) interval between first and last PSA values of ≥ 8 weeks but ≤ 12 months as stated in PCWG3 guidelines (Scher et al., 2016; Pound et al., 1999).

If the baseline PSA value prior to first dose of randomized treatment is missing or < 0.2 ng/mL, PSA doubling time will be missing.

For interpretation of PSA doubling time it should be noted that PCWG3 guidelines state the calculation should be based on the most recent PSA values during androgen deprivation therapy. These additional criteria will not be applied.

- PSA response: PSA response is defined as the proportion of patients who have a $\geq 50\%$ decrease in PSA from baseline that is confirmed by a second PSA measurement ≥ 4 weeks later. All scheduled and unscheduled PSA assessments will be used to determine and confirm PSA response.
- PSA $> 80\%$ decrease: PSA $\geq 80\%$ decrease is defined as the proportion of subjects that have a $\geq 80\%$ decrease in PSA from baseline that is confirmed by a second PSA

measurement ≥ 4 weeks later. All scheduled and unscheduled PSA assessments will be used to determine and confirm a PSA $\geq 80\%$ decrease.

- Duration of PSA response (only for patients with response) (months): (date of PSA progression/censor – Date of PSA response + 1)/30.4375. Duration of PSA response is defined as the duration (in months) between the date of first document PSA response (i.e. $\geq 50\%$ decrease in PSA from baseline) and earliest date of PSA progression as defined above. The censoring date is the date of last PSA assessment.

